12.1 FUNDING SOURCE22

12.2 CONFLICT OF INTEREST23

12.3 SUBJECT STIPENDS OR PAYMENTS.....23

13 REFERENCES.....24

List of Abbreviations

ACRONYM	DESCRIPTION
ACOG	American College of Obstetrics and Gynecology
AE	Adverse event
ALT	Alanine aminotransferase
ANOVA	Analysis of variance
APGAR	APGAR score
AST	Aspartate aminotransferase
B ₃ A	B ₃ -amide
BP	Blood pressure
BPP	Biophysical profile
CBC	Complete blood count
CRF	Case report form
CT	Computerized tomography
CTCA v3.0	Common terminology criteria for adverse events v3.0
DSMB	Data Safety and Monitoring Board
EOP	Early onset preeclampsia
EFW	Estimated fetal weight
ET	Endothelin
GI	Gastrointestinal
HELLP	Hemolysis, elevated liver enzymes, low platelets
HIV	Human immunodeficiency virus
INH	Isoniazid
LFTs	Liver function tests (includes AST and ALT)
MRI	Magnetic resonance imaging
MVP	Maximum vertical pocket
MWF	Monday, Wednesday, Friday
NIH	National institutes of health
PHI	Personal health information
NICU	Neonatal intensive care unit
NIH	National institutes of health
NST	Non-stress test
PHI	Protected health information
pK	Pharmacokinetics
PIGF	Placental growth factor
PI	Principal investigator
P/C	Protein to creatinine ratio
RDA	Recommended daily allowance
sFlt-1	Soluble fms-like tyrosine kinase-1
SD	Standard deviation
TID	Three times per day
UA	Umbilical artery
ULN	Upper limit of normal
VEGF	Vascular endothelial growth factor
WHO	World Health Organization

Study Summary

Title	A PHASE II STUDY OF VITAMIN B ₃ AMIDE DIETARY SUPPLEMENTATION IN WOMEN WITH EARLY CONSET PREECLAMPSIA
Short Title	NicPreDose
Protocol Number	001v7
Phase	Phase II
Methodology	Open label
Study Duration	24 months
Study Center(s)	University of North Carolina Women's Clinic/Hospital
Objectives	
 1. To test the effects of a novel oral agent, nicotinamide, on mean arterial pressure (MAP) after 48 hours and 7 days of treatment; 2. To measure safety of nicotinamide in women with early-onset preeclampsia (n=25). Safety defined as development of maternal liver toxicity, defined as $\geq 3x$ ULN of ALT or AST while on treatment, defined as within 24 hours of dose; 3. To determine maternal tolerability of nicotinamide 2.5 gm/day, administered as 1000mg at 8AM and 12MN; 500mg at 4PM 4. To measure pharmacokinetics (pK) of nicotinamide 1000 mg in normal healthy reproductive age women (n=6) and healthy, normotensive pregnant women (n=6).
Number of Subjects	37 (25 preeclamptic; 6 non-pregnant; 6 healthy, normotensive, pregnant)

Diagnosis and Main Inclusion/Exclusion Criteria
	
Diagnosis and Inclusion Criteria for women with severe preeclampsia
 
• Maternal age 18-45 years• Singleton or twin pregnancy with no known fetal anomalies• Early-onset preeclampsia defined as:
○ Early-onset: between 24 weeks 0 days and -33 weeks 3 days, based on menstrual dating confirmed by first or second trimester ultrasound OR second trimester ultrasound if menstrual dating unavailable;○ Preeclampsia:
▪ New onset hypertension and proteinuria, with systolic BP \geq 140 mm Hg and/or diastolic BP \geq 90 mm Hg on two occasions 6 hours apart and > 300 mg proteinuria on 24 hour urine collection OR urine P/C ratio >0.3;▪ New onset hypertension and NO proteinuria, with systolic BP \geq 140 mm Hg and/or diastolic BP \geq 90 mm Hg on two occasions 6 hours apart and one or more of the following: serum creatinine >1.1 mg/dL or doubling from baseline ,or central nervous system symptoms or visual changes▪ Severe gestational hypertension defined as new onset systolic BP \geq 160 mm Hg and/or diastolic BP \geq 105.○ Candidate for expectant management for at least 48 hours○ Deemed clinically stable by primary clinician and candidate for expectant management (delayed delivery) for at least 48 hours;• Maternal liver function tests < 2x ULN• Maternal platelet count \geq 100,000 mm³• Planned expectant management• Pre-existing medical diseases such as hypertension, diabetes, endocrine disorders, gastrointestinal diseases, are well controlled• Fetal well-being established by estimated fetal weight \geq 5th %tile; normal amniotic fluid volume (MVP \geq 2 cm); normal UA Dopplers; or reactive NST or BPP > 6• Delivery not anticipated within 48 hours of enrollment 
Exclusion Criteria for women with severe preeclampsia
 
• Pre-existing renal disease (creatinine \geq 1.5 mg/dL)• Any pre-existing medical condition that would increase risk for liver toxicity (e.g. hepatitis B or C; HIV; INH use)• Eclampsia; cerebral edema on CT/MRI; headache unrelieved by analgesics• Evidence of liver dysfunction (LFTs \geq 2x ULN)• Thrombocytopenia (platelets < 100,000 mm³)• Pulmonary edema• HELLP syndrome• Evidence of fetal compromise: EFW < 5th percentile; or BPP < 6; or absent or reverse diastolic UA blood flow; or oligohydramnios (MVP < 2 cm)
--	---

	
• Placental abruption defined as unexplained vaginal bleeding• Preterm labor defined as regular contractions and cervical change• Any condition deemed by the investigator to be a risk to mother or fetus in completion of the study• Any condition deemed by the investigator to require delivery within 48 hours 
Inclusion Criteria for healthy, normotensive, pregnant women
 
• Maternal age 18-45 years• Singleton or twin pregnancy with no known fetal anomalies (24 weeks to 33 weeks 3 days)• No known medical complications 
Exclusion Criteria for healthy, normotensive, pregnant women
 
• Current cigarette smoker• Hypertension requiring medical treatment• Diabetes requiring medical treatment• Pre-existing renal disease (creatinine \geq 1.5 mg/dL)• Any pre-existing medical condition that would increase risk for liver toxicity (e.g. hepatitis B or C; HIV; INH use)• Currently taking medication for a chronic medical condition• Currently taking an oral or IV antibiotic or antifungal medication 
Diagnosis and Inclusion Criteria for healthy nonpregnant women
 
• Age 18-45 years• No known medical complications or disease (eg hypertension, diabetes, liver or kidney disease) 
Exclusion Criteria for healthy nonpregnant women
 
• Current cigarette smoker• Hypertension requiring medical treatment• Diabetes requiring medical treatment• Pre-existing renal disease (creatinine \geq 1.5 mg/dL)• Any pre-existing medical condition that would increase risk for liver toxicity (e.g. hepatitis B or C; HIV; INH use)• Currently taking medication for a chronic medical condition (excluding oral contraceptives)• Currently taking an oral or IV antibiotic or antifungal medication
--	---

Study Product, Dose, Route, Regimen
	
Vitamin B₃-amide; 2.5 mg daily, administered as 1000mg at 8AM and 12MN; 500mg at 4PM, provided by Major Pharmaceuticals
 
[name] Advisor, Contracts and Billing [name] [name] Office: [contact] [contact] Email: [contact]

Duration of administration
	
Until delivery or 34 weeks' gestation


Statistical Methodology
	
Primary Outcome
 
• Mean arterial blood pressure before, 48 hours, and 7 days after daily dosing 
Secondary Outcomes
 
• Maternal liver toxicity: the proportion of women who develop elevated liver function tests (ALT and/or AST \geq 3x ULN within 24 hours of study drug) will be determined and compared to expected proportion of 20%• Maternal side effects (nausea, vomiting, rash, headache)• Optional: Plasma nicotinamide and 2-pyridone levels; sFlt-1 and PIGF levels

1. Introduction

This document is a protocol for a human research study. This study is to be conducted according to US and international standards of Good Clinical Practice (FDA Title 21 part 312 and International Conference on Harmonization guidelines), applicable government regulations and Institutional research policies and procedures.

1.1 Background

Preeclampsia is a hypertensive disorder unique to pregnancy that occurs in approximately 5 – 8% of pregnancies in the United States.¹ The disease is mild in 75% of cases, and 10% of cases occur before 34 weeks' gestation.² Despite its relatively rare prevalence, preeclampsia is the **leading cause** of maternal morbidity and mortality in the United States. Worldwide, 10 to 15% of direct maternal deaths (i.e., resulting from obstetric complications of pregnancy) are associated with preeclampsia/eclampsia.³ Women who develop preeclampsia are at risk for pulmonary edema⁴, coagulation defects, hepatic and/or renal failure, seizures, cerebral hemorrhage, and blindness.⁵⁻⁷

In 2013 ACOG published an Executive Summary from the Task Force on Hypertension in Pregnancy. They proposed the following for the diagnosis of preeclampsia:

- Blood pressure greater than or equal to 140 mm Hg systolic or greater than or equal to 90 mm Hg diastolic on two occasions at least 4 hours apart after 20 weeks of gestation in a woman with a previously normal blood pressure; or greater than or equal to 160 mm Hg systolic or greater than or equal to 110 mm Hg diastolic, within a short interval (minutes) to facilitate timely antihypertensive therapy

AND

- Proteinuria, defined as \geq to 300 mg per 24-hour collection (or this amount extrapolated from a timed collection) or protein/creatinine ratio \geq 0.3, or urine dipstick reading of 1+ (if other quantitative methods not available)

OR

- New-onset hypertension and no proteinuria with the new onset of any of the following: platelet count less than 100,000/microliter, creatinine $>$ 1.1 mg/dL or doubling from baseline, elevated LFTs $>$ 2xULN, pulmonary edema, CNS symptoms, or visual changes.

Preeclampsia is also a significant contributor to neonatal morbidity and mortality. Fetal complications are not uncommon and include poor fetal growth from chronic placental hypoperfusion⁸, especially in cases of early-onset preeclampsia.^{9, 10} Placental abruption, premature separation of the placenta with disruption of blood flow to the fetus, is an uncommon but life-threatening complication that occurs in up to 3% of pregnancies complicated by severe preeclampsia.¹¹

There are no proven measures to treat preeclampsia; resolution occurs only with delivery. In early onset preeclampsia ($<$ 34 weeks), delaying delivery and prolongation of pregnancy is of benefit to the fetus but potentially detrimental to the mother. Medically indicated preterm birth as a secondary result of fetal or maternal complications contributes significantly to neonatal morbidity and mortality associated with preeclampsia.¹² As shown in Figure 1, **preeclampsia is**

one of the leading causes of medically indicated preterm birth. Conservatively estimated, > 20,000 preterm births < 34 weeks occur annually in the United States due to complications of preeclampsia. A therapeutic approach to early-onset preeclampsia to prolong pregnancy that will do no harm to both the mother and fetus is an important and unmet med.

The pathophysiology of preeclampsia is complex and incompletely understood. Activation of several different pathways is thought to be operative in the development of preeclampsia. Evidence exists to support excessive maternal inflammation¹³ maternal immunologic responses¹⁴, placental hypoxia and oxidative stress¹⁵, generalized vasospasm, and alteration of growth factor production, as part of the pathophysiologic process in preeclampsia. The sentinel paper by Roberts et. al.¹⁶ implicated angiogenic imbalance with endothelial activation and generalized maternal endothelial dysfunction as the explanation for most of the clinical aspects of preeclampsia. These pathways are all believed to culminate in endothelial activation and dysfunction¹⁷, characterized by an imbalance between circulating pro- and anti-angiogenic factors.

Angiogenesis requires the complex interplay between vascular endothelial growth factor (VEGF), placental growth factor (PlGF), and their receptors, soluble fms-like tyrosine kinase-1 (sFlt-1) and VEGFR-1. The placenta is a rich source of these factors, and in addition to regulating vascular homeostasis, VEGF, PlGF, and sFlt-1 are key components in regulating trophoblast cell function and survival.¹⁸⁻²⁰ sFlt-1 acts as an anti-angiogenic factor by neutralizing PlGF and VEGF.²¹

Animal and laboratory data exist to support the theory of angiogenesis imbalance as the root cause of preeclampsia. Overexpression of sFlt-1 induces hypertension and fetal growth restriction in pregnant mice, and the time course of blood pressure increase mirrors the increase in sFlt-1.²² The preeclampsia-like clinical phenotype associated with sFlt-1 expression occurs via activation of the endothelin (ET) system.^{23, 24} In humans, low plasma vascular endothelial growth factor (VEGF) in the first trimester of pregnancy is a predictive marker for preeclampsia. In addition, sFlt-1/PlGF ratios are increased in women who subsequently develop preeclampsia compared to normotensive women.²⁵ ~90% of women with EOP have elevated sFlt-1.²⁶ An sFlt-1/PlGF ratio >0.85 is associated with adverse pregnancy outcomes: placental abruption, elevated liver enzymes and/or low platelets, and small-for-gestational-age birth weight and/or absent/reversed umbilical artery Doppler, and significantly shorter latency period, among women with EOP. 75% of women with sFlt-1/PlGF >0.85 deliver within one week and 85% within two weeks, compared to only 10% and 15% of women with sFlt-1/PlGF <0.85. sFlt-1/PlGF is a useful discriminator for women with EOP who are at risk for adverse outcome and need for delivery prior to 34 weeks.²⁷ The natural history of circulating sFlt-1 levels among women with preeclampsia has been described in several longitudinal studies.^{28, 29} sFlt-1 levels are elevated prior to the development of clinical symptoms of preeclampsia, and remain elevated until delivery.¹⁷ Based on this data, we believe that elevated circulating sFlt-1 levels identify those women at greatest risk for adverse outcome, particularly if managed expectantly, and thus the women most likely to yield benefit from treatments that allow for longer latency.

To address the angiogenic imbalance believed to be in the pathophysiology of preeclampsia, we²⁴ and others³⁰⁻³³ have demonstrated that ET receptor antagonists greatly ameliorate the preeclampsia-like phenotypes induced by sFlt-1 in animal models. While this data is promising, ET receptor antagonists are teratogenic and contraindicated in pregnant

[figure not shown]
[figure not shown]

Figure 1. Percent of medically indicated preterm birth (PTB) due to preeclampsia (PEX), fetal distress, small for gestational age (SGA), and abruption

women. However, this does not preclude the use of substances that block the action of factors downstream of the ET receptor that would mediate sFlt-1 expression and action.

Following this reasoning,

we tested the effects of nicotinamide, the amide of vitamin B₃ (B₃A) a potent inhibitor of ADP ribosyl cyclase (ADPR cyclase). ADPR cyclase is activated by endothelin, and mediates an increase in cytosolic Ca²⁺ and vasoconstriction. Using our mouse model of sFlt-1 overexpression, we found that nicotinamide ameliorates the increased BP and urinary albumin excretion induced by increased sFlt-1. In our mouse

Legend: [control]: mice receiving neither virus nor vitamin B₃. [sFlt-1]: mice receiving sFlt-1 virus but not given vitamin B₃ (n=5); [sFlt-1 + Nic (d0)]: mice given vitamin B₃ daily starting on the same day as they received the virus (n=6); [sFlt-1 + Nic (d7)]: mice treated with vitamin B₃ starting 7 days after they received the virus.

studies we used 500mg/kg/day, equivalent to 41mg/kg/day in humans, which would be 2.7g/day for an average adult with a weight of 60kg. As shown in the Figure on the following page, we found a significant lowering of urinary albumin excretion, increase in open capillary volume on renal histopathology, and lowering of blood pressure, when vitamin B₃A was given to mice as preventive (Nic (d0) group) or as therapeutic (Nic (d7) group) treatment. **Panel a** shows urinary excretion of albumin normalized to urinary creatinine concentration. **Panel b** shows open capillary volume on renal histopathology. **Panel c** shows systolic blood pressure (SBP) measured by telemetry.

1.2 Investigational Agent

The investigational agent for this protocol is Vitamin B₃ Amide (B₃A; Nicotinamide)

Chemical Formula: C₆-H₆-N₂-O. Metabolites include N1-methylnicotinamide and its oxidation products.

Niacin (nicotinic acid, vitamin B₃) is an essential vitamin. Vitamin B₃ and the amide form have identical vitamin functions, but vitamin B₃-amide does not have the same pharmacological and toxic effects as vitamin B₃. Thus it does not reduce cholesterol or induce flushing.³⁴ In cells, vitamin B₃ is incorporated into nicotinamide adenine dinucleotide (NAD) and NAD-phosphate, which are coenzymes in a wide variety of oxidation-reduction reactions.³⁵

The U.S. Recommended Daily Allowance (RDA) for niacin is 18 mg/day during pregnancy and 17 mg/day during lactation. The recommended upper limits for pregnant and lactating women are 30 – 35 mg/day.³⁶ Prenatal vitamins contain 14-18 mg of niacin.

1.3 Preclinical Data

The LD₅₀ of vitamin B₃-amide in rodents is 3-7g/kg when given orally³⁷, and its therapeutic index is correspondingly wide.

Ieraci et al.³⁸ have shown that a single high dose of vitamin B₃-amide protects mice from developing the neurological damage and behavioral abnormalities that occur in adults that were exposed to high doses of alcohol perinatally at the time when the developing nervous system is most susceptible to chemical damage. The control mice given vitamin B₃-amide but no alcohol were indistinguishable neurologically and in behavior from the mice given saline. Thus vitamin B₃-amide is harmless to mice exposed to it at a dose level and at a time when it is highly protective against damage from alcohol.³⁸

Vitamin B₃-amide has also been shown to protect rat pups from long-term neurologic effects of perinatal asphyxia.³⁹

1.4 Clinical Data to Date

Vitamin B₃-amide has several properties that may be of clinical benefit to patients. Vitamin B₃-amide has been used clinically to treat acne vulgaris⁴⁰, anxiety and schizophrenia⁴¹, Alzheimer's disease^{42, 43} and cancer.⁴⁴ Vitamin B₃A has been used for long periods without significant side effects at doses of 50mg/kg/day for a variety of conditions, including type 1 diabetes and schizophrenia.^{45, 46} Use of high dose vitamin B₃-amide to treat schizophrenia was not associated with any embryonic or fetal toxicity among women who experienced pregnancy while on treatment⁴⁶, based on exposure of 3 pregnant women. Human data demonstrate a risk for jaundice of 1 in 2000 following high dose vitamin B₃-amide treatment for psychosis.⁴⁷

Studies in children have been conducted to prevent insulin-dependent diabetes. In a population-based diabetes prevention trial, 173 school age children with islet cell antibodies received vitamin B₃-amide treatment (500 mg BID) for 2.7 years. Side effects, liver function abnormalities, and growth were recorded. There were no reactions or toxicity ascribed to vitamin B₃-amide treatment.⁴⁸ In another study, vitamin B₃-amide at a dose of 1.2 g/m²/day or placebo was given to children age 3-12 years who were at risk for Type I diabetes. While vitamin B₃-amide failed to reduce the cumulative diabetes incidence at 3 years, no side effects were observed in the children receiving vitamin B₃-amide. Body growth was compared and decrease in growth was not observed in children receiving vitamin B₃-amide compared to placebo.⁴⁹

In a clinical trial of vitamin B₃-amide versus placebo for diabetes prevention, 276 subjects were randomized to 1.2 g/m² per day of vitamin B₃-amide.⁵⁰ Regular safety analyses done throughout the trial showed no differences between the treatment groups with respect to adverse events. 35 serious adverse events were reported in 18 participants in the active treatment group and 15 in the placebo group. Increased LFTs (> 3x ULN) were noted in nine participants during the trial. Of these, five were taking active treatment group and four were on placebo. Six women became pregnant during the trial, four in the vitamin B₃A group and two in placebo. Trial medication was stopped as soon as pregnancy was confirmed. No congenital abnormalities were reported in the offspring.⁵⁰

3.1 General Design

This is an open labeled phase II study of vitamin B₃-amide dietary supplementation in pregnant women with early-onset preeclampsia, per ACOG guidelines. We will enroll 24 pregnant women at 24-33 weeks 3 days with EOP and anticipated treatment by expectant observation. If the woman is anticipated to remain undelivered for 48 hours after diagnosis she will receive vitamin B₃-amide, 2.5 mg/day dosed in the following manner: administered as 1000mg at 8AM and 12MN; 500mg at 4PM, continuing until delivery or 34 weeks, whichever occurs first. Optional research blood samples will be collected at times of clinically indicated blood draws (baseline and 2-3 times per week) to measure nicotinamide and its metabolite 2-pyridone, sFlt-1 and PIGF. A sample of cord blood will be collected (6ml) following delivery.

All study subjects will receive standard surveillance and treatment for expectant management of EOP, which may include but is not limited to:

- Daily prenatal vitamin
- 24-hr urine collection for protein excretion at admission
- Blood sampling for hematologic, liver, and kidney function at time of diagnosis and every 2-3 days thereafter
- Magnesium sulfate for seizure prophylaxis
- Betamethasone to accelerate fetal lung maturity
- Antihypertensive agents
- Twice weekly fetal surveillance by NST (30 minutes of continuous fetal heart rate monitoring) or BPP (30 minutes of ultrasound to monitor for fetal breathing, movement, fluid)
- Weekly ultrasound to measure amniotic fluid and UA Dopplers

In addition to above standard care for EOP, subjects will receive surveillance and treatment solely for study purposes, including:

- Daily administration of vitamin B₃-amide, 2.5 Gm/day in 3 divided doses; "on treatment" is defined as within 24 hours of dose
- Daily (M-F) study staff visit to query side effects if in-patient; with each outpatient visit (typically twice a week) if discharged from the hospital
- Optional blood sampling to coincide with clinical blood draws to measure sFlt-1, nicotinamide and 2-pyridone levels; chart abstraction to review liver function testing results (done clinically)
- Chart abstraction for maternal and delivery data (up until maternal discharge) and neonatal data (until 30 days of age or until discharge, whichever occurs first). We will

also perform a phone call at 30 days post stopping the study medication and 30 days following infant delivery to determine the occurrence of any adverse events. In addition to enrolling women with early-onset severe preeclampsia we will enroll 12 healthy control women (6 non pregnant, and 6 pregnant between 24-33 weeks 3 days). Study staff will interview control women and confirm medical history consistent with no exclusions. Once enrolled, healthy participants will have a baseline blood sampling for nicotinamide levels and LFTs. They will then ingest 1000 mg nicotinamide, and have blood drawn 2, 8 and 24 hours following the dose of nicotinamide. Urine samples will also be collected at baseline, and at 8 and 24 hours following the dose of nicotinamide. Participants will be given the option to remain in the clinic for the 2- and 8-hour blood collection and then return the following day for the 24 hour blood collection, or to be admitted to the UNC Clinical and Translational Research Center for all blood collection.

3.2 Study Outcomes

PRIMARY

- Maternal mean arterial blood pressure, defined as the highest MAP within 24 hour period

SECONDARY-SAFETY AND TOLERABILITY

- Liver toxicity, defined as 3x ULN of ALT or AST within 24 hours of study drug
- Maternal report of side effects
- Clinical parameters of maternal and fetal well being
- Composite neonatal outcome

Maternal or Fetal Parameter	Safety Endpoint
History	Headache unrelieved by oral analgesics
Physical examination	Abdominal tenderness, (right upper quadrant or epigastric)
Vaginal bleeding	Fall in hematocrit of $\geq 3\%$
Urine output	Oliguria (< 500 cc/24 hr)
Serum LFTs	AST and/or ALT $\geq 3x$ ULN within 24 hours of study drug
Fetal NST (or BPP)	Category III (or < 6)

SECONDARY-PHARMACOKINETICS

- Nicotinamide and metabolite concentrations in plasma at baseline, 2, 8, and 24 hours
- Peak plasma drug and metabolite concentration and time to reach peak
- Nicotinamide and metabolite elimination half-life
- Nicotinamide and metabolite area under the curve (integral of the plasma concentration-time curve)
- Nicotinamide and metabolite concentrations in urine at baseline, 8 and 24 hours

4 Subject Selection and Withdrawal

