4.1 Inclusion Criteria for participants with early-onset preeclampsia

1. Maternal age 18-45 years
2. Singleton or twin pregnancy with no known fetal anomalies
3. Early-onset preeclampsia OR early-onset severe gestational hypertension
 - a. Early onset defined as 24-33 weeks 3 days gestation
 - b. Preeclampsia defined as new onset hypertension and proteinuria: systolic BP ≥ 140 mm Hg and/or diastolic BP ≥ 90 mm Hg on two occasions 6 hours apart and > 300 mg proteinuria on 24 hour urine collection OR urine P/C ratio > 0.3 ;

- c. Or BP \geq 160 mm Hg and/or diastolic BP \geq 105
- d. Dating criteria based on menstrual dating confirmed by first or second trimester ultrasound OR second trimester ultrasound if menstrual dating unavailable;
- e. Deemed clinically stable by primary clinician and candidate for expectant management (delayed delivery) for at least 48 hours;
- f. Dating criteria based on menstrual dating confirmed by first or second trimester ultrasound OR second trimester ultrasound if menstrual dating unavailable;
4. Deemed clinically stable by primary clinician and candidate for expectant management (delayed delivery);
5. Pre-existing medical diseases such as hypertension, diabetes, endocrine disorders, gastrointestinal diseases, are well controlled
6. Maternal liver function tests $<$ 2x ULN
7. Maternal platelet count \geq 100,000 mm³
8. Fetal well-being established by estimated fetal weight \geq 5th %tile; normal amniotic fluid volume (MVP \geq 2 cm); normal UA Dopplers; AND reactive NST or BPP $>$ 6
9. Plan for expectant management until delivery
10. Delivery not anticipated within first 48 hours

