- Blood sampling at baseline (pre-dose), 2 hours post dose, 8 hours post dose and 24 hours post dose.
- Urine sample at baseline (pre-dose), 8 hours post dose and 24 hours post dose.
- This will be done either in the clinic or the CTRC

6.3 **Laboratory specimen handling procedures**

Blood for research purposes will be collected at the time of clinically indicated blood draws. Specimens will be labeled with the subject's unique study ID and processed.

Specimens to be tested for circulating sFlt-1 and PlGF levels will be stored and shipped as a single batch on dry ice to the research laboratory at Harvard University. The interassay coefficient of variance for sFlt1 and PlGF immunoassays ranges from 2.6% to 3.0%.

Specimens collected for nicotinamide and 2-pyridone measurements will be sent to the UNC School of Pharmacy Lab ([name]). [name] developed a LC-MS/MS method using protein precipitation (acetonitrile) to measure nicotinamide and 2-pyridone during our previous phase I study.

7 **Statistical Plan**

7.1 **Statistical Methods**

Sample size: The study sample size was calculated to the primary outcome of MAP. We stipulated *a priori* that $\alpha = .05$ and $\beta = 0.2$. Using the highest BP measured within each 24-hr period and applying the following formula we will calculate daily MAP:

$$\text{mean arterial BP} = [2(\text{diastolic BP}) + \text{systolic BP}] \div 3$$

Assuming that the mean (\pm sd) MAP at enrollment of our subjects is 107 (\pm 10) mm Hg, to detect a difference from enrollment to 48 hours after treatment of 7 mm Hg in MAP requires that 20 subjects be enrolled. We will enroll 24 to allow for 20% attrition due to delivery prior to 48 hours of treatment.

- We will use a repeated measurement ANOVA to compare baseline MAP to MAP at 48 hours, 7 days and weekly thereafter until delivery or 34 weeks.
- Maternal liver toxicity: the proportion of women who develop elevated liver function tests (ALT and/or AST \geq 3x ULN within 24 hours of study drug) will be determined and compared to expected proportion of 20%.
- Descriptive report of proportion of women with
 - Side effects
 - Fetal effects

7.2 **Subject Population(s) for Analysis**

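### The primary outcome is a 24-hour maximum of MAP with no fixed number of readings, so MAP at day 7 can fall after discharge simply because fewer readings are taken

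*Combined protocol and SAP*

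**What the plan says.** The outcome definition in section 3.2 is "Maternal mean arterial blood pressure, defined as the highest MAP within 24 hour period". Section 7.1 puts it slightly differently: "Using the highest BP measured within each 24-hr period and applying the following formula we will calculate daily MAP". The sample size is set "to detect a difference from enrollment to 48 hours after treatment of 7 mm Hg in MAP", on the assumption that "MAP at enrollment of our subjects is 107" with an SD of 10 mm Hg. The analysis is also in 7.1: "We will use a repeated measurement ANOVA to compare baseline MAP to MAP at 48 hours", with 7 days and later weeks to follow.

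The Study Summary makes day 7 a stated time point as well. The first objective is "To test the effects of a novel oral agent, nicotinamide, on mean arterial pressure (MAP) after 48 hours and 7 days of treatment", and the primary outcome is listed as "Mean arterial blood pressure before, 48 hours, and 7 days after daily dosing".

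Four features of the plan bear on this:

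- Entry on blood pressure (4.1) needs 140 systolic and/or 90 diastolic "on two occasions 6 hours apart", or a severe-range pressure.
- Women may be discharged on treatment and are then seen about twice a week (3.1).
- Antihypertensives are left to the primary clinician (5.5).
- The only untreated comparison is each woman's own baseline. The healthy women take a single dose for pharmacokinetics.

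No section states how many pressures are taken in a 24-hour window or asks for equal numbers across windows. None says whether the baseline window includes the qualifying pressures. Section 4.4.2 places the primary outcome at 72 hours, not 48.

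**The concern.** The expected value of an average does not depend on how many readings go into it. The expected value of a maximum does. A woman whose pressure is monitored often as an in-patient and only occasionally after discharge will tend to show a lower maximum later, even if her underlying pressure has not moved. More readings later would do the opposite and hide a real fall.

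Baseline is the second route. If the window contains the raised pressures that brought the woman into the study, later values will on average be lower without any treatment effect.

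With no concurrent untreated women, neither shift cancels out. The first objective is the effect of nicotinamide on MAP, so the change from baseline will be read as a drug effect. The design effect is 7 mm Hg, and a spurious shift of 2 or 3 mm Hg is a material part of that.

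**Working it through.** **Inputs.** From 7.1: alpha .05, beta .2, enrolment MAP 107 (SD 10), effect 7 mm Hg, 20 women needed, 24 enrolled. Assumed, because the documents give no figures: normally distributed readings, reading SD (σ) of 5 to 8 mm Hg, and the reading counts below.

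**1. The plan's own figure.** Use a paired t test, two-sided .05, with 10 taken as the SD of the change. (The plan states 10 as the SD at enrolment, so this is an assumption.) The noncentrality is 7√n/10. Power is 79.9% at n = 18, 82.3% at n = 19 and 84.4% at n = 20. The smallest n reaching 80% is 19, so the stated 20 is consistent. For attrition, 20 × 1.2 = 24.

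**2. Effect of the reading count alone.** For k independent readings, E[max] = μ + σ·e(k), where e(k) = ∫ x·k·φ(x)·Φ(x)^(k−1) dx. This gives e(12) = 1.629, e(6) = 1.267, e(3) = 0.846 and e(1) = 0.

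| Readings, baseline to later | Difference in e(k) | Shift at σ = 5 | Shift at σ = 8 |
|---|---|---|---|
| 12 to 6 | 0.362 | 1.8 mm Hg | 2.9 mm Hg |
| 6 to 3 | 0.421 | 2.1 mm Hg | 3.4 mm Hg |
| 6 to 1 (extreme) | 1.267 | 6.3 mm Hg | 10.1 mm Hg |

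Reversing the counts reverses the sign. Correlation between readings shrinks the shift: at 0.5 between readings two hours apart, 12 to 6 gives 1.467 − 1.197 = 0.270 SD, or 1.35 to 2.16 mm Hg. The last row shows only how fast the effect grows; the documents do not say that an out-patient has one reading.

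**3. What such a shift does to the test.** Take n = 20, SD of change 10, and a paired t test standing in for the repeated-measures comparison. The noncentrality is shift × √20/10, and the nominal rate of significant falls is 2.5%.

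| Shift (mm Hg) | Significant fall, no true change | Power for a true fall of 7 if the shift is upward |
|---|---|---|
| 0 | 2.5% | 84.4% |
| 1.35 | 8.3% | 66.9% (7 − 1.35 = 5.65) |
| 1.81 | 11.7% | 59.6% (7 − 1.81 = 5.19) |
| 2.90 | 23.3% | 41.3% (7 − 2.90 = 4.10) |

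These rates are conditional on a count imbalance that the documents do not show at 48 hours. They also depend on the SD of change: a smaller SD gives higher false-fall rates. No rate is given for day 7, where fewer women remain undelivered and the SD of change is unknown.

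**4. Baseline and the qualifying pressures.** With equal counts and qualifying pressures that precede the baseline day, simulation gives a change of about zero. With the qualifying pair inside the baseline day, one set of assumptions (MAP only; screened mean 95 to 100; within-person SD 3 to 7; 2 to 6 readings) gave a spurious fall of 0.2 to 4.1 mm Hg. Another, with systolic and diastolic modelled separately, gave 0.5 to 3.2, but it needed a low screened mean diastolic of 60 to 72. Both show the direction; neither is an estimate for this trial.

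**5. Highest MAP or highest BP.** Section 3.2 takes the highest MAP; 7.1 puts the highest BP into the MAP formula. MAP increases with both components. If the highest systolic and highest diastolic come from different readings, the 7.1 value equals or exceeds the 3.2 value. The text does not say which is meant.

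**The case against.** The strongest reply is that this is a limit of the design, not of the endpoint wording. A reader might infer that the undefined counts and window are why alpha = .05 is not assured for a drug effect. The documents do not support that. The alpha in 7.1 is attached to a change in MAP from enrolment. A drug effect is not isolated mainly because there is no untreated preeclampsia arm and antihypertensives are discretionary. Equal counts and a clean baseline would leave both in place. What stands is that the count and baseline biases are additional and avoidable.

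Three further inferences are tempting and also fail:

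- *That the 48-hour result is biased towards a false fall.* The twice-weekly visits in 3.1 apply after discharge. Nothing shows that counts differ at 48 hours, and the direction is open.
- *That the assumed mean of 107 shows baseline overlaps the qualifying pressures.* A reading of 140/90 has MAP (2 × 90 + 140)/3 = 106.7, but entry is on systolic and/or diastolic, so this is not a MAP cut-off: 140/75 gives 96.7 and 125/90 gives 101.7. The severe-range 160/105 gives 123.3. A mean of 107 fits a later or treated baseline at least as well.
- *That the report could never show what happened.* Section 9.2 lists hospital records and office charts as source documents, so charted counts and times can be recovered. The plan does not ask for them.

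It is also fair that baseline is not wholly undefined: the plan says before dosing and at enrolment. What is missing is the limits of the window. None of this answers the day-7 problem, where the stated rule itself makes the result depend on how many readings were taken.

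**Conclusion.** The concern holds in a limited form. An uncorrected daily maximum, compared within woman, depends on the reading count, and the plan's own visit schedule makes lower counts plausible at day 7. The illustrative shift is 1.8 to 2.9 mm Hg for 12 to 6 readings and 2.1 to 3.4 for 6 to 3, against a design effect of 7. That rests on independent normal readings with an SD of 5 to 8, none of which the documents give. At 48 hours, the sample-size time point, a bias is possible but not shown, in either direction. Regression to the mean adds to the fall only if baseline includes the qualifying pressures; otherwise it contributes about nothing. These biases come on top of the single-arm limits, which no endpoint wording removes. The point should be corrected, but it does not invalidate the sample size.

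**What to change.** In 3.2 and 7.1:

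- Compute MAP from the systolic and diastolic values of one reading.
- Take baseline from pre-dose readings after the qualifying pressures. Flag women for whom this is not possible, and prespecify a sensitivity analysis without them.
- Use the same prespecified number of charted readings at baseline, 48 hours and 7 days. If the maximum over all readings stays primary, add two prespecified companion analyses: the maximum over an equal count, and the average of those same readings.
- Report the number of readings per window.
- State that a fall of a few mm Hg cannot be attributed to nicotinamide from this test alone.
- Reconcile the primary time point: 48 hours in 7.1, 72 hours in 4.4.2.

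This uses pressures already charted and needs no added arm or change in care. The costs are more chart abstraction and some women missing from the equal-count analysis at day 7, probably those discharged. Where only a same-day baseline exists, some fall may remain: 0.4 to 2.3 mm Hg in simulation with 2, 3 or 5 readings per window, under assumed variability. The SD of 10 must also be re-justified if the reading count changes.
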